8.1.2 Laboratory test abnormalities

8.1.2.1 Definitions and reporting

Laboratory abnormalities that constitute an Adverse event in their own right (are considered clinically significant, induce clinical signs or symptoms, require concomitant therapy or require changes in study treatment), should be recorded on the Adverse Events eCRF. Whenever possible, a diagnosis, rather than a symptom should be provided (e.g. anemia instead of low hemoglobin). Laboratory abnormalities that meet the criteria for Adverse Events should be followed until they have returned to normal or an adequate explanation of the abnormality is found. When an abnormal laboratory or test result corresponds to a sign/symptom of an already reported adverse event, it is not necessary to separately record the lab/test result as an additional event.

Laboratory abnormalities that do not meet the definition of an adverse event should not be reported as adverse events. A Grade 3 or 4 event (severe) as per CTCAE does not automatically indicate a SAE unless it meets the definition of serious as defined below and/or as per investigator's discretion. A dose hold or medication for the lab abnormality may be required by the protocol in which case the lab abnormality would still, by definition, be an adverse event and must be reported as such.

8.2 Serious adverse events

8.2.1 Definitions

Serious adverse event (SAE) is defined as one of the following:

- Is fatal or life-threatening
- Results in persistent or significant disability/incapacity
- Constitutes a congenital anomaly/birth defect
- Is medically significant, i.e., defined as an event that jeopardizes the patient or may require medical or surgical intervention to prevent one of the outcomes listed above
- Requires inpatient hospitalization or prolongation of existing hospitalization,
- Note that hospitalizations for the following reasons should not be reported as serious adverse events:

- Routine treatment or monitoring of the studied indication, not associated with any deterioration in condition (i.e. to perform study related assessments)
- Elective or pre-planned treatment for a pre-existing condition that is unrelated to the indication under study and has not worsened since signing the informed consent
- Social reasons and respite care in the absence of any deterioration in the patient's general condition
- Note that treatment on an emergency outpatient basis that does not result in hospital admission and involves an event not fulfilling any of the definitions of a SAE given above is not a serious adverse event

8.2.2 Reporting

To ensure patient safety every SAE, regardless of suspected causality, occurring after the patient has provided informed consent and until at least 30 days after the patient has stopped study treatment must be reported to Novartis within 24 hours of learning of its occurrence.

Any additional information for the SAE including complications, progression of the initial SAE, and recurrent episodes must be reported as follow-up to the original episode within 24 hours of the investigator receiving the follow-up information. A SAE occurring at a different time interval or otherwise considered completely unrelated to a previously reported one should be reported separately as a new event.

Any SAEs experienced after the 30 day safety evaluation follow-up period should only be reported to Novartis if the investigator suspects a causal relationship to the study treatment.

Information about all SAEs is collected and recorded on the Serious Adverse Event Report Form; all applicable sections of the form must be completed in order to provide a clinically thorough report. The investigator must assess and record the relationship of each SAE to each specific study treatment (if there is more than one study treatment), complete the SAE Report Form in English, and submit the completed form within 24 hours to Novartis. Detailed instructions regarding the SAE submission process and requirements for signatures are to be found in the investigator folder provided to each site.

Follow-up information is submitted in the same way as the original SAE Report. Each reoccurrence, complication, or progression of the original event should be reported as a followup to that event regardless of when it occurs. The follow-up information should describe whether the event has resolved or continues, if and how it was treated, whether the blind was broken or not, and whether the patient continued or withdrew from study participation.

If the SAE is not previously documented in the [Investigator's Brochure] or Package Insert (new occurrence) and is thought to be related to the Novartis study treatment, an oncology Novartis Chief Medical Office and Patient Safety (CMO&PS) department associate may urgently require further information from the investigator for Health Authority reporting. Novartis may need to issue an Investigator Notification (IN), to inform all investigators involved in any study with the same drug that this SAE has been reported. Suspected Unexpected Serious Adverse Reactions (SUSARs) will be collected and reported to the competent authorities and relevant ethics committees in accordance with Directive 2001/20/EC or as per national regulatory requirements in participating countries.

8.3 Emergency unblinding of treatment assignment

Not Applicable.

8.4 Pregnancies

This trial is planned for men, post-menopausal women or premenopausal women with ovarian suppression, so no pregnancies are expected for study patients. However, in the rare cases when this occurs, to ensure patient safety, each pregnancy occurring while the patient is on study treatment must be reported to Novartis within 24 hours of learning of its occurrence. The pregnancy should be followed up to determine outcome, including spontaneous or voluntary termination, details of the birth, and the presence or absence of any birth defects, congenital abnormalities, or maternal and/or newborn complications.

Pregnancy should be recorded on a Clinical Trial Pregnancy Form and reported by the investigator to the oncology Novartis Chief Medical Office and Patient Safety (CMO&PS). Pregnancy follow-up should be recorded on the same form and should include an assessment of the possible relationship to the study treatment any pregnancy outcome. Any SAE experienced during pregnancy must be reported on the SAE Report Form.

Pregnancy outcomes should be collected for the female partners of any males who took study treatment in this study. Consent to report information regarding these pregnancy outcomes should be obtained from the mother.

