Study treatment discontinuation	Point/time when patient permanently stops taking study treatment for any reason.
Subject Number	A unique identifying number assigned to each patient/subject/healthy volunteer who enrolls in the study
Supportive treatment	Refers to any treatment required by the exposure to a study treatment, e.g. premedication of vitamin supplementation and corticosteroid for pemetrexed disodium.

Glossary of terms

Confidential

Treatment group	A treatment group defines the dose and regimen or the combination, and may consist of 1 or more cohorts. Cohorts are not expanded, new cohorts are enrolled.			
Variable	Identifier used in the data analysis; derived directly or indirectly from data collected using specified assessments at specified timepoints			
Withdrawal of Consent	Jrawal of Consent Withdrawal of consent occurs only when a patient does not want to particip the study any longer, and does not want any further visits or assessments, does not want any further study related contact			

Protocol summary

Title	An open-label, multicenter, Phase IIIb study to assess the safety and efficacy of ribociclib (LEE011) in combination with letrozole for the treatment of men and pre/postmenopausal women with hormone receptor-positive (HR+) HER2-negative (HER2-) advanced breast cancer (aBC) with no prior hormonal therapy for advanced disease		
Brief title	Study to assess the safety and efficacy of ribociclib (LEE011) in combination with letrozole for the treatment of men and pre/postmenopausal women with HR+ HER2- aBC in a broader population		
Sponsor and Clinical Phase	Novartis Phase IIIb		
Investigation type	Drug		
Study type	Interventional		
Purpose and rationale	The purpose of this Phase IIIb study is to collect additional safety and efficacy data for the combination of ribociclib + letrozole in a broader population of patients with HR+HER2- aBC in comparison with other Phase III studies with ribociclib.		
Primary Objective(s) and Key Secondary Objective	To evaluate the safety and tolerability of ribociclib with letrozole in men and pre/postmenopausal women with HR+, HER2- aBC who received no prior hormonal therapy for advanced disease Note: Throughout this document, perimenopausal and premenopausal status will be grouped together and referred as "Premenopausal"		

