1.2.1.1 Non-clinical data

Ribociclib inhibits the phosphorylation of Rb at CDK4/6-binding sites with an average IC50 of 60 nM in Jeko-1 MCL cells that overexpress cyclin D1. Regardless of the various genetic aberrations that may be present in the cancer cells, the anti-tumor activity of ribociclib requires the presence of functional pRb.

Cardiac safety studies *in vivo* demonstrated QT prolongation with the potential to induce premature ventricular contractions (PVCs) at higher exposure levels. The effects of ribociclib on the bone marrow (hypocellularity), lymphoid system (lymphoid depletion), intestinal mucosa (atrophy), the kidney (concurrent degeneration and regeneration of tubular epithelial

cells), skin (atrophy), bone (decreased bone formation) and testes (atrophy) are considered to be related to the pharmacological inhibition of cell replication in these tissues due to CDK4/6 inhibition. The hepatobiliary system (proliferative changes, cholestasis, sand-like gallbladder calculi and inspissated bile) was identified as an additional target organs of toxicity that are not likely related to the primary pharmacology of ribociclib. Generally, all these effects of ribociclib demonstrated either reversibility or a clear trend towards reversibility. Ribociclib did not show an indication for a genotoxic potential. Reproductive studies in animals have demonstrated that ribociclib is embryotoxic, fetotoxic and teratogenic.

In vitro, ribociclib was a reversible inhibitor of human cytochrome P450 (CYP) enzymes CYP1A2, CYP2E1 and CYP3A4 and a time-dependent inhibitor of CYP3A4. Under therapeutic conditions, inhibition of CYP3A4 is likely to occur, while inhibition of CYP1A2 or CYP2E1 is not expected. The *in vitro* inhibitory potency of ribociclib for the transporters breast cancer resistance protein (BCRP), organic cation transporter 2 (OCT2), multidrug and toxin extrusion protein-1 (MATE1), and bile salt export pump (BSEP) may translate into clinically relevant inhibition at therapeutic doses.

Elimination of ribociclib is dominated by oxidative metabolism mainly via CYP3A4 with a minor contribution by flavin-containing monooxygenase 3 (FMO3). Although ribociclib is a substrate of the P-glycoprotein (P-gp) efflux transporter, this process is likely not clinically relevant due to the high passive permeability of ribociclib.

Refer to the most recent ribociclib [Investigator's Brochure] for additional details.

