 - Concomitant medications, herbal supplements, and/or fruits (e.g. grapefruit, pomelos, star fruit, Seville oranges) and their juices that are known strong inducers or inhibitors of CYP3A4/5 (See Appendix 14.1)
 - Medications that have a narrow therapeutic window and are predominantly metabolized through CYP3A4/5

- 15. Patient is currently receiving or has received systemic corticosteroids ≤ 2 weeks prior to starting study drug, or who have not fully recovered from side effects of such treatment. Note: The following uses of corticosteroids are permitted: single doses, topical applications (e.g., for rash), inhaled sprays (e.g., for obstructive airways diseases), eye drops or local injections (e.g., intra-articular)
- 16. Participation in a prior investigational study within 30 days prior to enrollment or within 5-half-lives of the investigational product, whichever is longer
- 17. Pregnant or nursing (lactating) women

Note: Women of child-bearing potential, defined as all women physiologically capable of becoming pregnant, unless they are using highly effective methods of contraception during dosing and for 21 days after stopping the study medication.

Highly effective contraception methods include:

- Total abstinence when this is in line with the preferred and usual lifestyle of the patient. Periodic abstinence (e.g. calendar, ovulation, symptothermal, post-ovulation methods) and withdrawal are not acceptable methods of contraception.
- Female sterilization (have had surgical bilateral oophorectomy with or without hysterectomy), total hysterectomy or tubal ligation at least 6 weeks before taking study treatment. In case of oophorectomy alone, only when the reproductive status of the woman has been confirmed by follow up hormone level assessment.
- Male partner sterilization (at least 6 months prior to screening). For female patients on the study the vasectomized male partner should be the sole partner for that patient.
- Placement of an intrauterine device (IUD) or intrauterine system (IUS)

Note: Use of oral (estrogen and progesterone), transdermal, injected, implanted hormone containing intrauterine systems (IUS) or any other hormonal methods of contraception is not allowed in this study

6 Treatment

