7.2.2 Safety and tolerability assessments

Safety will be monitored by assessing physical exam, vital signs, hematological and chemistry labs as well as collecting of the adverse events at every visit during Core Phase (Table 7-1). For patients who continue study participation during Extension Phase, (S)AEs and related

assessments and, pregnancy test will be performed (Table 7-2). For details on AE collection and reporting, refer to Section 8.

Premenopausal women must complete the following pregnancy tests:

- Screening Serum pregnancy test done locally
- Every 4 weeks during treatment urine pregnancy test. Can be administered at patient's home
- End of Treatment visit serum pregnancy test done locally

Premenopausal women who administer urine pregnancy testing at home should complete a simple diary with the dates and the outcome of the urine pregnancy tests while on study treatment. In case of a positive pregnancy test, the instructions in Section 8.4 should be followed.

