8.1 Adverse events

8.1.1 Definitions and reporting

An adverse event is defined as the appearance of (or worsening of any pre-existing) undesirable sign(s), symptom(s), or medical condition(s) that occur after patient's signed informed consent has been obtained.

Abnormal laboratory values or test results occurring after informed consent constitute adverse events only if they induce clinical signs or symptoms, are considered clinically significant,

require therapy (e.g., hematologic abnormality that requires transfusion or hematological stem cell support), or require changes in study medication(s).

Adverse events that begin or worsen after informed consent should be recorded in the Adverse Events eCRF. Conditions that were already present at the time of informed consent should be recorded in the Medical History page of the patient's eCRF. Adverse event monitoring should be continued for at least 30 days (or 5 half-lives, whichever is longer) following the last dose of study treatment. Adverse events (including lab abnormalities that constitute AEs) should be described using a diagnosis whenever possible, rather than individual underlying signs and symptoms. When a clear diagnosis cannot be identified, each sign or symptom should be reported as a separate Adverse Event.

Adverse events will be assessed and graded according to the Common Terminology Criteria for Adverse Events (CTCAE) version 4.03. Grade 1 to 5 will be used to characterize the severity of the Adverse Event.

If CTCAE grading does not exist for an adverse event, the severity of mild, moderate, severe, and life-threatening, death related to the AE corresponding to Grades 1 - 5, will be used. Information about any deaths (related to an Adverse Event or not) will also be collected though a Death form.

The occurrence of adverse events should be sought by non-directive questioning of the patient (subject) during the screening process after signing informed consent and at each visit during the study. Adverse events also may be detected when they are volunteered by the patient (subject) during the screening process or between visits, or through physical examination, laboratory test, or other assessments. As far as possible, each adverse event should be evaluated to determine:

- 1. The severity grade (CTCAE Grade 1-5)
- 2. Its duration (Start and end dates)

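### Section 8.4 requires a pregnancy report only for pregnancies during study treatment, although the protocol's contraception, AE and SAE periods all run past the last dose

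*Protocol*

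**What the plan says.** For female patients, Protocol Section 8.4 sets the duty in one sentence: "each pregnancy occurring while the patient is on study treatment must be reported to Novartis within 24 hours of learning of its occurrence". Follow-up to determine the outcome, and the dedicated pregnancy form, attach to those pregnancies. No post-dose period is given. For female partners of male patients, the same section asks for outcomes with no time limit.

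Other sections do look past the last dose:

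- **Contraception.** Exclusion criterion 17 (Section 5.3, with the same period in the Protocol summary) expects women of child-bearing potential to use "highly effective methods of contraception during dosing and for 21 days after stopping the study medication".
- **Basis for concern.** Section 1.2.1.1: "Reproductive studies in animals have demonstrated that ribociclib is embryotoxic, fetotoxic and teratogenic".
- **AEs.** Section 8.1.1: "Adverse event monitoring should be continued for at least 30 days (or 5 half-lives, whichever is longer) following the last dose of study treatment".
- **SAEs.** Section 8.2.2 covers every SAE from consent "until at least 30 days after the patient has stopped study treatment must be reported to Novartis within 24 hours". Later SAEs are reported only when the investigator suspects that study treatment caused them.
- **Testing.** Section 7.2.2 lists three kinds of test for premenopausal women: serum at screening, urine every four weeks on treatment, and last "End of Treatment visit serum pregnancy test done locally". Table 7-1 places that visit within 7 days of the last dose and lists no pregnancy test at the 30-day safety follow-up.
- **Safety follow-up.** Section 7.1.7 sends the data from that contact to the adverse event and concomitant medication pages and does not mention pregnancy.

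**The concern.** The protocol has a specific reason to want data on pregnancies exposed to ribociclib, and it has a form and a follow-up procedure for them. The trigger for that procedure stops at the end of treatment, while three related duties continue. A site that follows Section 8.4 exactly has no duty to report an uncomplicated pregnancy conceived shortly after the last dose, and no duty to find out how it ended.

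What would be lost is small but hard to recover: a handful of exposed or possibly exposed pregnancies, including those with a normal outcome. If only the adverse outcomes come in, through SAE reporting, they come without the uneventful pregnancies needed to interpret them. The rule is also narrower for women who took the drug than for partners of men who took it.

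**Working it through.** There is no planned figure to reproduce. The check compares periods, with one side calculation on half-life.

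**1. Periods after the last dose**

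| Duty | Period after last dose | Source |
|---|---|---|
| Pregnancy report and outcome follow-up, female patients | none stated (0 days) | Protocol 8.4 |
| Contraception | 21 days | Protocol 5.3, criterion 17; Protocol summary |
| AE monitoring | at least 30 days, or 5 half-lives if longer | Protocol 8.1.1 |
| SAE reporting, any cause | at least 30 days | Protocol 8.2.2 |
| Last scheduled pregnancy test | within 7 days | Protocol 7.2.2, Table 7-1 |
| Outcomes in partners of male patients | no limit stated | Protocol 8.4 |

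Gap against contraception: 21 − 0 = 21 days. Gap against AE/SAE follow-up: at least 30 − 0 = 30 days. Days without a scheduled test, inside the contraception period: at least 21 − 7 = 14 days (days 8 to 21).

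**2. Can ribociclib still be present in the gap?** Section 1.2.1.2.3 gives an effective half-life of 32.0 h, range 8.06 to 97.9 h. Five half-lives in days = 5 × half-life ÷ 24:

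- shortest: 5 × 8.06 = 40.3 h = 1.7 days
- central: 5 × 32.0 = 160 h = 6.7 days
- longest: 5 × 97.9 = 489.5 h = 20.4 days

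So a conception in the first week after the last dose could be exposed in a typical patient, and one in the third week only in a patient near the top of the range. All three values lie below 30 days, so for ribociclib the 30-day floor governs the AE period. The protocol does not say how the 21 days were derived.

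**3. Which pregnancies fall outside the rule?**

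- *Conceived on treatment, found on treatment or at EOT:* covered by 8.4.
- *Conceived on treatment, found after EOT:* covered. The pregnancy occurred during treatment, and the 24-hour clock starts when the site learns of it.
- *Conceived after the last dose, with an SAE within 30 days, or a later SAE suspected to be causal:* the SAE is reportable under 8.2.2. Section 8.2.1 counts as serious any event that "Constitutes a congenital anomaly/birth defect".
- *Conceived after the last dose, no reportable SAE:* no duty to report and no duty to follow to outcome. This is the gap.

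**4. Does another definition of treatment close it?** The glossary entry for discontinuing study treatment reads "Point/time when patient permanently stops taking study treatment for any reason". Section 8.4 cites no other definition.

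**The case against.** **The phrase may be meant more broadly.** Section 10.5.3.1 and SAP Section 2.1.3 define an on-treatment period that ends 30 days after the last administration (except for Core Phase patients moving to the Extension). Study treatment includes goserelin or leuprolide, and SAP Section 2.4.1.2 counts exposure to these until 27 days after the last injection. This shows that zero days may not have been intended. It does not settle the matter: these are analysis definitions that Section 8.4 does not cite, the glossary ends treatment when the patient stops taking it, and Section 8.2.2 writes out its post-dose period where one is wanted.

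**A contraception period and a reporting trigger serve different purposes.** They do, and they can differ without contradiction. A reader might infer that the protocol itself defines 21 hazardous days, or that drug persists throughout them. It states only a precautionary contraception period, and 20.4 days is the extreme half-life case. The point rests on the missing post-dose period, not on 21 days being a measured risk window.

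**Other routes catch some cases.** They do. A reader might infer that every such pregnancy would go unreported and be lost. The documents support only that no report is required: an SAE would come in, and a site may report voluntarily. But births generally fall well after day 30, when a birth defect is reportable only if the investigator suspects causality, and an uneventful pregnancy triggers nothing.

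**Too early to detect at EOT.** A reader might also infer that a pregnancy conceived on treatment and missed at EOT escapes the rule. It does not; that is a limit of scheduled detection, not of the reporting duty.

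**Few patients remain.** Amendment 04 records the Core Phase as complete and 415 patients in the Extension. The number of premenopausal women among them is not given. This limits the yield of a change.

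**Conclusion.** The point holds as a minor gap in safety data collection. Section 8.4 as worded does not require reporting or outcome follow-up of a pregnancy that a female patient conceives after her last dose, unless it leads to a reportable SAE, although the protocol's contraception period runs 21 days and its AE and SAE periods at least 30 days beyond that dose.

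Ovarian suppression and required contraception make events rare; the documents give no rate, so no expected count is offered. No primary or secondary endpoint, analysis set or estimate changes.

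The conclusion rests on two assumptions: that treatment in Section 8.4 has its glossary meaning, and that no period is set in material outside these documents, such as the pregnancy form or the consent form. It concerns female patients only. There is one related case. Section 6.3.2 foresees patients who leave study treatment but go on taking ribociclib from another source, with safety follow-up of up to 30 days. A pregnancy conceived then would be on the drug but, read literally, not on study treatment.

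**What to change.** Reconcile Section 8.4 with criterion 17 (Section 5.3 and the Protocol summary) and with Sections 8.1.1 and 8.2.2, so that 8.4 states an explicit post-dose period for reporting and outcome follow-up that is consistent with the protocol's own post-dose periods. Which period applies is for the sponsor to decide and justify, since the existing ones differ (21 days and at least 30 days). The sentence should also say whether patients continuing ribociclib outside the trial are included.

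Record pregnancy status for premenopausal women at the existing 30-day safety follow-up, in both phases, and add this item to Section 7.1.7 and Tables 7-1 and 7-2.

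The content is one amended sentence and one added question at a contact that already takes place. No dose or treatment rule changes. The formal cost is a written amendment with the approvals listed in Section 12.1, so it is best carried with the next amendment made for other reasons.
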